**I. Purpose, Background and Rationale**

**A. Aim and Hypotheses**

The pedagogy of weight management education has received little investigation, despite health education being considered an essential aspect of weight loss interventions. We propose a 24-week study in which adults will engage in weekly, group weight management classes via Zoom utilizing the flipped classroom teaching methodology. All participants will receive a standard weight management diet and exercise prescription. The aims of this study are to:

1. Determine the feasibility and effectiveness of a 24-week, weight management intervention in adults (ages 18-75) for improving lifestyle habits and weight reduction
2. Measure changes in weight, physical activity, and behavioral outcomes across a 24-week weight management intervention

**B. Background and Significance**

There is an overall lack of pedagogy (i.e., approaches to teaching and learning) behind weight management programs. We have conducted multiple searches in NIH RePORTER and PubMed and have found no studies on pedagogy for weight management education, despite educational content being a staple in weight management interventions and programs (Franz et al., 2007; Maula et al., 2020). Investigation of pedagogy in weight management education is virtually absent in the literature and it is warranted to investigate given the rising obesity epidemic.

An educational model used in academic institutions, deemed the active learning model, may serve as a feasible educational model used in weight management interventions. In a traditional education model, the educator reviews educational materials during class times, then the students independently complete skills-based homework assignments outside of class (Ayaz & Sekerci, Oct 2015; Mayasari et al., Mar 2018; Persky & McLaughlin, 2017). In contrast, the active learning model requires students to independently review educational material before class, and class time with the educator is spent engaging in group and individual skills-based activities and problem-solving assignments (Ayaz & Sekerci, Oct 2015; Mayasari et al., Mar 2018; Persky & McLaughlin, 2017). The theoretical basis for the development of active learning is to elicit higher cognitive learning, according to the revised Bloom's taxonomy (Bloom et al., 1956; Krathwohl, 2002) and shift independent student time to passive learning (remembering and understanding) and collaborative student and educator time to active learning (applying, analyzing, evaluating, and creating) (Krathwohl, 2002). When utilized in academic institutions, the active learning model has been shown to increase student test scores, learning, engagement, and skill acquisition across a variety of health and science- related topics (McLaughlin et al., 2014; Persky & McLaughlin, 2017; Simpson & Richards, 2015).

Investigators believed mechanisms behind the improvement in student learning were ownership of learning and flexibility (Simpson & Richards, 2015), self-efficacy and preparation (Alt, 2015; McLaughlin et al., 2014), and self-awareness and problem-solving (Freeman et al., 2014). Previous research shows enhanced weight loss with improved self-efficacy (Nezami et al., 2016) and self-awareness via self-monitoring (Painter et al., May 2017) in adults during a weight management intervention, supporting the inference that an educational model with outcomes which enhance student learning in academic institutions may be an effective pedagogy for weight management education.

### **C. Rationale**

Establishing effective weight management education techniques may help improve intervention adherence and improve lifestyle habits that can assist with long-term weight reduction.

## **II. Research Plan and Design**

### **A. Study Objectives**

The purpose of this study is to examine the feasibility and initial efficacy of a pedagogy applied in a weight management intervention for adults with overweight/obesity.

### **B. Study Type and Design**

This study is a 24-week, single-arm trial investigating the feasibility of a flipped classroom behavioral intervention for weight management. We will recruit up to 30 adults ages 18+ with a body mass index greater than or equal to 25 kg/m^2 to participate in weekly, 1-hour group weight management education delivered remotely via Zoom with a trained health educator. Participants will receive a dietary prescription of 1200-1500 calories/day (5 portion-controlled meals and 5+ servings of fruits and vegetables) and exercise prescription of 150-300 minutes exercise/week. Additionally, participants will be asked to self-monitor diet and exercise adherence weekly. Feasibility outcomes will be collected at baseline, 12-weeks, and 24-weeks.

### **C. Subject Criteria**

*Inclusion:* 1) Body Mass Index greater than or equal to 25 kg/m^2. 2) Age: 18-75 yrs. 3) Wireless internet connection in the home. 4) Ability to engage in moderate to vigorous exercise. *Exclusion:* 1) Unable to commit to weekly group education. 2) Food allergy/intolerance that would hinder ability to adhere to dietary prescription.

### **D. Specific methods and techniques used throughout the study**

#### **1. Intervention:**

*Virtual, group instruction:* Participants will be complete a total of 24, 1-hour group education sessions with a trained health educator. The group size will be 15-18 participants with continuous recruitment until reaching a total of 30 participants. Sessions will be delivered virtually (Zoom®). Prior to each group meeting, participants will be provided hard copy and audio/visual versions (podcasts and YouTube®) of the lesson to be covered in the upcoming meeting. group session will follow a pre-determined structure: group discussion, review of adherence, 5 to 10 minutes of physical activity, and an active learning-based education. Thus, active learning-based education will include: case vignettes, group debates/discussions, think-pair-share activities, gamification of health-related topics, creation of meal and physical activity, problem-solving barriers to a healthy diet and physical activity, and hands-on worksheets.

- i. Diet Prescription. Participants will receive a diet prescription of 1200-1500 kilocalories (kcals), consisting of 5 portion-controlled meals [(PCMs); 3 shakes and 2 entrees], 5 servings of fruits and vegetables, and zero-calorie beverages. All PCM shakes will be prescribed from the company Health Management Resources (HMR), consisting of 100 kcals and 10g of protein/shake. PCM entrees are available either via HMR or approved outside entrees for purchase at the grocery store as determined by the RD. Guidelines for the approved outside entrees are <300 kcals, <10g sugar, and <3g saturated fat per PCM. Participants will be encouraged to consume at least 65 ounces of zero-calorie beverages per day. Adherence to the diet prescription will be monitored via weekly self-monitoring sheets submitted to the RD by email prior to the educational session for review and feedback.
- ii. Exercise Prescription. Participants will be asked to engage in 45 minutes of moderate- to-vigorous exercise 5 days per week or 50,000 steps per week. A pedometer will be available for purchase if desired, but participants may use personal step counting devices (e.g.,

phone apps, watches). Adherence to the prescribed MVPA and steps will be assessed using weekly self-monitoring sheets submitted to the RD via email prior to each session.

## 2. Schedule of Evaluations

	Screening Visit: (Day-30 to Day-1)	Baseline (Day-30 to Day-1):	Weekly	End of Study (Week 24)
Informed Consent	X			
Enrollment	X			
Anthropometrics	X		X	
Health History		X		X
Quality of Life		X		X
Self-Efficacy		X		X
Diet Behaviors		X		X
Session Attendance			X	
Diet Adherence			X	
Exercise Adherence			X	

## 3. Description of Evaluations

a. Anthropometrics (Weight, Height, Waist Circumference): Participants will be weighed at the KU Weight Management Clinic location in Kirmayer Fitness Center on the main KU Medical Center campus. Anthropometrics will be collected in a private room by a registered nurse prior to the participant seeing a clinic physician. Weight will be collected to the nearest 0.1 kg. Standing height will be measured using a stadiometer. Body Mass Index will be calculated as weight (kg) divided by height (cm) squared. Waist circumference will be measured at the midline level between the inferior margin of the ribs and the superior border of the iliac crest.

b. Health History: A health history developed by the study team will be completed online via the REDCap database. Questions include a comprehensive assessment of previous weight loss attempts, current and previous medical conditions, current medications, and previous medical procedures.

c. Quality of Life: Quality of life will be assessed using the Short Form 36 Health Survey Questionnaire (SF-36). The SF-36 is a validated and commonly utilized survey ( $\alpha > 0.85$ ) that relies on self-report of 8 domains: limitations in physical activities because of health problems, limitations in social activities because of physical or emotional problems, limitations in usual role activities because of physical health problems, bodily pain, general mental health, limitations in usual role activities because of emotional problems, vitality, and general health perceptions (Brazier et al., 1992).

d. Self-Efficacy: Self-efficacy will be assessed using two tools: the Health Eating and Weight Self-Efficacy (HEWSE) scale and the Self-Efficacy for Exercise (SEE) scale. Both surveys will be completed at baseline and post-intervention via REDCap. The HEWSE is an 11-item scale to measure healthy eating and weight-selficacy with good internal consistency ( $\alpha > 0.80$ ) and test-re-test reliability ( $r = 0.72$ ) (Wilson-Barlow et al., 2014). The SEE is a 9-item scale that measures confidence engaging in exercise 3 times per week for 20 minutes ( $\alpha = 0.9$ ) (Resnick & Jenkins, 2000).

- e. **Diet Behaviors:** Diet behaviors will be assessed using the Eating Attitudes Test, 26-item version (EAT-26) completed via REDCap survey. The EAT-26 is a self-report of general and risky eating behaviours as a screening measure for disordered eating behaviors (Garner et al., 1982) that clinicians can use as a screening tool prior to engaging in a lifestyle intervention.
- f. **Session Attendance:** Attendance to the group education sessions will be measured weekly and evaluated by the health educator. Attendance records will be entered into the study REDCap database.
- g. **Diet Adherence:** Adherence to the diet prescription will be measured weekly via participant self-report. Participants will report daily total number of shakes, number of entrees, servings of fruit and vegetables, and days off plan. The self-monitoring sheet will be submitted via email to the health educator prior to each group session. The health educator will provide individual feedback based on self-reported diet adherence.
- h. **Exercise Adherence:** Adherence to the exercise prescription will be measured weekly via participant self-report. Participants will report daily minutes of moderate to vigorous physical activity and steps. The self-monitoring sheet will be submitted via email to the health educator prior to each group session and individual feedback will be provided.

#### **F. Risk/Benefit Assessment**

Risks to the participant from participation in this study are minimal. Participants will be cleared by a board-certified obesity physician to participate in moderate to vigorous exercise and follow the diet prescription. Participants will be asked to gradually increase their exercise by 15-20 minutes per week. The benefits to the participants are the well-established benefits of weight reduction, including reduced risk of chronic disease and improved health outcomes. The information obtained from this study will increase our understanding regarding pedagogy for weight management and its impact on intervention components, such as adherence. The risks to participants in this study are minimal while the benefits are large.

#### **G. Location Where Study Will Be Performed**

Research activities will take place at the University of Kansas Medical Center weight management clinic located in Kirmayer Fitness Center. All data will be saved on a KUMC redcap database, and all study related documents will be saved on a KUMC P-Drive.

#### **H. Assessment of Subject Safety and Development of a Data and Safety Monitoring Plan**

1. Elements of the plan include:
  - a. Persons/groups who will review the data (study team; independent safety monitor, data monitoring committee or formal DSMB): Study Team
  - b. Data/events that will be reviewed: Subject accrual (adherence to protocol regarding demographics, inclusion/exclusion) and Adverse Event Rates
  - c. Frequency of review: Monthly
  - d. Types of analyses to be performed: Means
  - e. Safety-related triggers that would cause the PI to stop or alter the study: The most likely scenario indicating the need to stop the investigation would be a failure to recruit or deliver the intervention as planned. Another issue relating to stopping rules for this trial would be new information. It is unlikely that any new information will become available during this trial that would necessitate stopping the trial
2. Data on adverse events will be reported monthly to the PI throughout this trial. We anticipate that most adverse events will be mild in nature and will allow a complete return to the same activities after a short period of time; that is, later that day or a day or two later.
3. We anticipate most adverse events (if not all) will allow a complete return to the same activities after a short period of time; that is, later that day or a day or two later. However, if a serious adverse event that prohibits participation moving forward, the participant will be terminated from the intervention.

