**Measurement and Reporting of Adverse Events**

Data on adverse events will be reported monthly to the PI throughout this trial. We anticipate that most adverse events will be mild in nature and will allow a complete return to the same activities after a short period of time; that is, later that day or a day or two later.

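### The safety plan reviews adverse event rates monthly, but no scheduled evaluation or weekly form asks about adverse events, so the rate is likely to be under-counted

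*Combined protocol and SAP*

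**What the plan says.** **What is to be reviewed.** In section II.H, the data and safety monitoring plan, the study team is to look at "Subject accrual (adherence to protocol regarding demographics, inclusion/exclusion) and Adverse Event Rates". The review interval is given as "Frequency of review: Monthly" and the analysis as "Types of analyses to be performed: Means". The subsection headed Measurement and Reporting of Adverse Events states that "Data on adverse events will be reported monthly to the PI throughout this trial" and adds an expectation that most events will be mild and brief. It names no question, recall window, responsible person or denominator.

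**What is to be collected.** The Schedule of Evaluations (II.D.2) has ten rows, from informed consent to "Exercise Adherence". None is for adverse events. The Description of Evaluations (II.D.3) itemises the weekly self-report. For diet, "Participants will report daily total number of shakes, number of entrees, servings of fruit and vegetables, and days off plan". For exercise, "Participants will report daily minutes of moderate to vigorous physical activity and steps". The nearest health item is the Health History, at baseline and week 24: "Questions include a comprehensive assessment of previous weight loss attempts, current and previous medical conditions, current medications, and previous medical procedures".

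**The concern.** A monthly adverse event rate needs a defined source of events. The plan commits to the rate and to its review, but no procedure in it is described as producing the count. As written, the numerator is whatever participants choose to mention.

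That matters more here because of the kind of event expected. Both section II.H and the adverse event subsection anticipate mild problems that are over within a day or two. These are the events most easily lost when nobody asks.

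Two things are at stake. First, a reassuring monthly review would be hard to interpret, because few recorded events could mean few events or little asking. Second, section V.A commits the team to examining what led to any lower-than-expected recruitment, attendance or adherence. A participant who cut back because of a symptom or injury would show on the weekly sheet only as days off plan or fewer minutes, with no field for the reason.

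**Working it through.** **Step 1. Trace every described contact after enrolment and ask whether it can supply a monthly count.**

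| Contact | Timing | Described content | Adverse event question? |
|---|---|---|---|
| Weekly diet sheet (II.D.3.g) | Weekly | Food counts, days off plan | No |
| Weekly exercise sheet (II.D.3.h) | Weekly | Activity minutes, steps | No |
| Anthropometrics (II.D.2, II.D.3.a) | Marked weekly | Weight, height, waist, taken privately by a nurse | No |
| Group session (II.D.1) | Weekly | Discussion, adherence review, activity, education | No |
| One-to-one meeting (II.D.1.b) | Monthly, baseline to Month 3 | Goals, Fitbit data, adaptations | No |
| Health History, SF-36, EAT-26 | Baseline and week 24 | Conditions, quality of life, disordered-eating screen | Not described as such |

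The first five rows give participants chances to volunteer an event. The one-to-one meetings stop at Month 3 of a 24-week study. The last row could reveal a lasting problem, but has no post-baseline reading before week 24. No row yields a complete monthly rate.

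**Step 2. Look for a figure to reproduce.** The documents give no expected event rate, capture proportion or safety threshold. What follows is illustration only; the values of *p* and *s* are assumptions.

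**Step 3. Show why a low count is ambiguous.** Let *n* = 30 (the recruitment goal in V.A), *p* the true share of participants with an event, and *s* the share of those recorded. Count one event per affected participant and treat capture as independent between participants.

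- Expected number recorded = *n* × *p* × *s*
- Chance of at least one record = 1 − (1 − *ps*)^*n*

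| *p* | *s* = 100% | *s* = 50% | *s* = 25% |
|---|---|---|---|
| 5% | 1.5; 79% | 0.75; 53% | 0.375; 31% |
| 10% | 3.0; 96% | 1.5; 79% | 0.75; 53% |
| 20% | 6.0; >99% | 3.0; 96% | 1.5; 79% |

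Each cell gives the expected number recorded and the chance of recording at least one. The diagonals are identical: 5% fully captured, 10% half captured and 20% one-quarter captured all give 1.5 expected records and a 79% chance of at least one. The recorded count depends only on the product *ps*, so it cannot separate the true rate from the capture proportion.

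**Step 4. What zero events would show.** With full capture, the one-sided 95% upper bound for zero events is 1 − 0.05^(1/*n*):

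- *n* = 30: 1 − 0.05^(1/30) = 9.5%
- *n* = 24 (the minimum analysed in V.A): 1 − 0.05^(1/24) = 11.7%

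With incomplete capture, this bounds *ps*, so the bound on *p* is that figure divided by *s*. For *n* = 30 it is 9.5% / 0.50 = 19% at half capture and 9.5% / 0.25 = 38% at one-quarter capture. The bound weakens, and it cannot be stated until *s* is known or assumed.

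**The case against.** The strongest reply is that this is a gap in description. The plan commits to monthly reporting to the PI, and a document that names no method does not show that none will be used. Staff have frequent contact with participants, including the weekly nurse measurement and the monthly meetings. An obesity physician clears participants beforehand. The consent pages are not in the text available for review and may tell participants whom to contact about a problem. The objectives in sections I.A and II.A and the go/no-go rule in V.A do not concern safety, so no primary result depends on this.

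Much of that stands, and it limits the point. A reader might infer that the weekly sheet is the only individual contact, so that events could surface only by email or in front of the group. The documents do not support that: the schedule marks anthropometrics weekly and section II.D.1.b describes individual meetings. A reader might also infer that tolerability is a stated study question. It is not. The description of risk as minimal is a risk/benefit judgment, not a hypothesis under test.

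What the reply does not remove is the mismatch within the plan. Contact is not a collection procedure, and a contact instruction in a consent form would still be spontaneous reporting. The weekly sheets are itemised, and their listed items do not include adverse events.

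**Conclusion.** The point holds as a gap between the safety plan and the data collection: a monthly rate is promised, and no described procedure asks for the events that make it up. Under-counting is likely. This is an inference from the absence of a question and the expectation of mild, short-lived events. A reader might go further and say that events certainly will be under-counted, or that zero recorded events would support no bound at all. Neither follows: staff may hear of events informally, and a bound exists for any assumed capture proportion, though a weaker one than under full capture.

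The size cannot be taken from the documents. Under the stated assumptions, halving capture halves the expected count and doubles the zero-event bound, from 9.5% to 19% with 30 participants. The conclusion does not rest on those values. The matter affects the interpretation of safety data, not the weight-loss estimate, the sample size or the decision rule, and is best treated as an inexpensive improvement.

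**What to change.** 1. Add one question to the existing weekly self-monitoring sheet: any new symptom, injury or illness this week, its date, and whether diet or exercise was changed or stopped because of it.
2. Add a weekly row for adverse events to the Schedule of Evaluations, and refer to the question in the subsection on measuring and reporting adverse events.
3. State in section II.H how the monthly rate is computed: either participants with at least one event over all enrolled participants, or events over participant-weeks of follow-up. The second suits the continuous recruitment described in II.D.1. Do not restrict the denominator to participants who returned a sheet, because that would drop people who stopped because of a problem.
4. Report the number of unreturned sheets beside each monthly rate, so that missing answers are not read as absence of events.

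The cost is one item on a form already planned for up to 30 × 24 = 720 participant-weeks, and a matching database field. The downsides are slightly more form burden and probably a higher reported event count. No clinical action rule is proposed.

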**Measurement and Reporting of Subject Accrual, Adherence to Inclusion/Exclusion Criteria**

Review of the rate of subject accrual and adherence to inclusion/exclusion criteria will occur monthly to assure that participants meet eligibility criteria.

**Measurement and Reporting of Adverse Events**

Data on adverse events will be reported monthly to the PI throughout this trial. We anticipate that most adverse events will be mild in nature and will allow a complete return to the same activities after a short period of time; that is, later that day or a day or two later.

**Measurement and Reporting of Participant Compliance to the Treatment Protocol**

Compliance to the program will be monitored by attendance to the group sessions. Compliance to the intervention protocol will be reviewed monthly by the PI.

